8.3.3 METRC Coordinating Center Reporting Responsibilities

As appropriate and per METRC policies, the Coordinating Center will send a copy of each report received about an event judged reportable to all clinical sites, with instructions for each to forward the report to their IRB.

Copies of the report will also be sent to the DoD, the Study PI, and to the Medical Monitor. The MCC will maintain a list of such events for reporting and review at Steering Committee meetings.

8.3.4 Department of Defense Reporting Requirements

The following are reporting requirements and responsibilities of the Principal Investigator to the United States Army Medical Research and Materiel Command's (USAMRMC) Office of Research Protections (ORP), Human Research Protection Office (HRPO).

- (1) The protocol will be conducted in accordance with the protocol submitted to and approved by the USAMRMC ORP HRPO and will not be initiated until written notification of approval of the research project is issued by the USAMRMC ORP HRPO.
- (2) Accurate and complete study records will be maintained and made available to representatives of the U.S. Army Medical Research and Materiel Command as a part of their responsibility to protect human subjects in research. Research records will be stored in a confidential manner so as to protect the confidentiality of subject information.
- (3) All unanticipated problems involving risk to subjects or others, serious adverse events related to participation in the study and subject deaths related to participation in the study will be promptly reported by [contact]), by email ([contact]), or by [contact]) to the USAMRMC, Office of Research Protections, Human Research Protection Office. A complete written report will follow the initial notification. In addition to the methods above, the complete report will be sent to the U.S. Army Medical Research and Materiel Command, ATTN: MCMR-RP, [name].

- (4) Suspensions, clinical holds (voluntary or involuntary), or terminations of this research by the IRB, the institution, the Sponsor, or regulatory agencies will be promptly reported to the USAMRMC ORP HRPO.
- (5) Any deviation to the protocol that may have an adverse effect on the safety or rights of the subject or the integrity of the study will be reported to the USAMRMC ORP HRPO as soon as the deviation is identified.
- (6) Major modifications to the research protocol and any modifications that could potentially increase risk to subjects will be submitted to the USAMRMC ORP HRPO for approval prior to implementation. All other amendments will be submitted with the continuing review report to the USAMRMC ORP HRPO for acceptance.
- (7) A copy of the approved continuing review report and the local IRB approval notification will be submitted to the USAMRMC ORP HRPO as soon as these documents become available. A copy of the approved final study report and local IRB approval notification will be submitted to the USAMRMC ORP HRPO as soon as these documents become available.
- (8) The knowledge of any pending compliance inspection/visit by the FDA, OHRP, or other government agency concerning this clinical investigation or research, the issuance of Inspection Reports, FDA Form 483, warning letters or actions taken by any Regulatory Agencies including legal or medical actions and any instances of serious or continuing noncompliance with the regulations or requirements that relate to this clinical investigation or research will be reported immediately to USAMRMC ORP HRPO.

Unanticipated problems involving risk to volunteers or others, serious, unexpected adverse events related to participation in the study and all volunteer deaths related to participation in the study will be promptly reported by [contact]), by e-mail ([contact]), or by [contact]) to the U.S. Army Medical Research and Materiel Command's Office of Research Protections, Human Research Protections Office. A complete written report will follow the initial notification. In addition to the methods above, the complete report will be sent to the U.S. Army Medical Research and Materiel Command, ATTN: MCMR-RPH, [name]

8.4 Reporting Pregnancy

N/A

8.5 Type and Duration of the Follow-up of Participants After Adverse Events

Study patients who experience an SAE will be followed until resolution of the event, and a final report will be submitted to the medical monitor, and the coordinating center.

8.6 Modifications of Study Agent(s)/Intervention(s) for a Participant

N/A

8.7 Halting Rules for the Protocol

N/A

8.8 Stopping Rules for an Individual Participant/Cohort

N/A

8.9 Premature Withdrawal of a Participant

A participant may be withdrawn from the study without consent if the sponsor decides to end the study. Other reasons for removing a participant without consent may include but are not limited to non-adherence with the protocol and/or therapy, and inappropriate behavior towards study personnel.

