Following 2-4 weeks of home PT (T1), the participant will be fitted with the IDEO and engage in four weeks of Post-IDEO PT at the study center. During these 4 weeks, adjustments to the brace will be made and the participants will learn how to optimize the use of the brace.

At the end of the four weeks of post-IDEO PT (T2), performance testing will be repeated and overall satisfaction with the device assessed. The purpose of these assessments is to measure any immediate gains in function. Participants will then be formally ‘discharged’ from the PRIORITI program. They will be given the number of the Study Site Orthotist to call if any concerns arise with the IDEO and its fit. The costs associated with all visits to the orthotist during the 12 month follow-up period will be covered by the study.

At 6 months following the completion of the PRIORITI program (T3), participants will be contacted by the Study Coordinator and asked to participate in a brief interview by phone. The main purpose of this phone call is to keep participants engaged in the study and motivate them to come back to the hospital for the final visit at 12 months. We will also use this opportunity to ask them questions about their functioning, satisfaction with the brace and use of services (overall and specific to the IDEO). This interview will last about 15 minutes. During the call the he coordinator will remind the participant of the 12 month follow up visit. If the participant is living outside of the research site area, the coordinator will inform the participant that travel expenses can be covered for the 12 month follow up visit. (See appendix K).

At 12 months following the completion of the PRIORITI program (T4), participants will be asked to return to the Study Center to repeat the performance tests and self reported measures of outcome and satisfaction with the IDEO. Additional questions regarding use of services (overall and specific to the IDEO) will also be asked.

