6.3 Participant Follow up and Data Collection

The follow up visit schedule for this study will be closely related to the timing of brace fitting and PT participation. Follow up will occur immediately following post-IDEO PT (T2), 6 months following completion of all PT (i.e. post PRIORITI) (T3), and 12 Months post PRIORITI (T4). Each visit will have an interval of time surrounding the ideal date for the visit during which the visit may be completed and the data included in the trial database. This interval is approximately 1-2 weeks before or after the ideal date for a visit.

The data collected at follow-up are described below. These data are summarized in Appendix C.

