6.3.6 Early Termination Visit

Should a participant terminate the study prematurely, if at all possible, all procedures required at the month 12 (T4) visit will be performed at his/her final visit.

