7.2 Physical Therapy Protocol. As indicated above, participants enrolled in PRIORITI will participate in the Return to Run physical therapy regimen. During Phase 1 (pre-IDEO) participants will engage in a home physical therapy program as prescribed by the study team for 2-4 weeks. During Phase 2 (post-IDEO), participants will receive 3 sessions of PT a week for an additional 4 weeks. Participants will be encouraged to test the IDEO under load in real world

conditions and report their experience to the study team. Each PT session will last for approximately 90 minutes. During phase 2, participants will be encouraged to complete home exercises to complement the therapy they are receiving in the clinic.

To help ensure standardization of the PT protocol across centers, several procedures will be put in place. *First*, the PTAs providing the pre-IDEO and post-IDEO physical therapy must have some documented training in sports medicine and experience working with limb trauma patients. They will be trained in the PT protocol at a 3-day training at the Center for the Intrepid in San Antonio. The 3 days will be devoted to the PT protocol with ample use made of demonstrations and practice sessions. As mentioned above, training videos will be produced and provided to the PTs or PTAs for reference. *Second*, the PTAs will be required to document the therapy provided at each session. This documentation will be reviewed on an ongoing basis by the investigators to assure the fidelity of the intervention. *Third*, the PTAs will participate in bi-weekly video conference calls together with [name] at which time individual cases will be reviewed and difficulties in providing the PT and keeping patients engaged in the program will be discussed.

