10.6 Analysis Plan

All analyses will be conducted under the supervision of our senior statistician, [name] and METRC's senior economist, [name].

Specific Aims #1 and #2: Assessing Immediate and Long-term Improvements in Functional Performance and Self-Reported Outcomes. As described above, one-sided paired t-tests will be used to test for improvements in outcomes at a specified point in time after enrollment as compared to baseline. Differences in means between follow-up and baseline will be reported along with 95% confidence intervals.

To the extent possible, we will explore how improvement correlates with characteristics of the participants, the type and extent of their injury, baseline measures of impairment, and the percent of pre and post IDEO PT sessions attended (as we expect some variation in adherence to the PT regimen). Differences in improvement will be examined using stratified analyses and regressions where the change in outcomes is the dependent variable. We will also conduct the analysis including and excluding participants who complete less than 1/3 of the PT sessions.

Specific Aim #3: Documenting Patterns of Use and Satisfaction with the IDEO. This aim is largely descriptive in nature. To the extent possible, patterns of use and satisfaction will be compared with other studies reported in the literature. Also, variations in device satisfaction will be modeled as a function of patient characteristics and baseline measures of impairment using the appropriate regression techniques.

Specific Aim #4. Assessing the Economic Impact of PRIORITI. Relative to standard of care (SOC), the PRIORITI program may increase or decrease costs of care. Provision of the IDEO device, the associated rehabilitation program, need for special shoe wear, and any adjustments, repairs or replacements needed during the lifetime of wear represent added costs relative to SOC. However, the PRIORITI program could potentially reduce certain types of resource use and costs relative to SOC. For example, if the IDEO device offers greater mobility (without use of ambulatory aids) or reduced pain, participants might decrease follow-up visits or use of pain medications relative to standard of care. Use of the IDEO could also lead to fewer delayed amputations. Labor force participation, return to duty, and productivity of participants enrolled in

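### Section 8.9 allows removal from the study for non-adherence with therapy without keeping outcome collection open, while the Section 10.6 adherence analysis needs those participants' outcomes

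*Combined protocol and SAP*

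**What the plan says.** Section 8.9 of the combined protocol and SAP covers withdrawal without the participant's consent. After sponsor termination it adds: "Other reasons for removing a participant without consent may include but are not limited to non-adherence with the protocol and/or therapy". The removal is from the study, not only from therapy. The section is permissive, gives no attendance threshold and is silent on later outcome visits. Section 8.10 gives replacement as not applicable.

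Section 10.6 relates improvement to the percentage of sessions attended, "as we expect some variation in adherence to the PT regimen", and continues: "We will also conduct the analysis including and excluding participants who complete less than 1/3 of the PT sessions".

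Section 6.3.6 provides that, for a participant who terminates early, "if at all possible, all procedures required at the month 12 (T4) visit will be performed at his/her final visit". Section 6.3 gives each visit an interval "during which the visit may be completed and the data included in the trial database". Its width is stated as follows: "This interval is approximately 1-2 weeks before or after the ideal date for a visit".

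Section 10.4 lists conduct measures against missing data and plans analyses under missing at random, with pattern-mixture and selection models for departures from it. The Retention section promises efforts to keep participants in the study.

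**The concern.** The tests for Aims 1 and 2 are one-sided paired comparisons with baseline, and there is no control group. A participant contributes only if a follow-up value exists. If the study removes people because they attended little therapy, the loss depends on adherence. If those people also improve less, the mean change among the rest is too favourable to the program.

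The adherence analysis suffers as well. Its purpose is to show how far the result depends on attendance. If the low attenders have no outcomes, the run that includes them contains few or none of them. It then agrees with the run that excludes them for that reason alone, and the agreement could be mistaken for robustness.

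**Working it through.** **1. The plan's own figure.** Section 10.2 states 80% power for a standardised paired effect of 0.28 with 80 complete participants. With n = 80 the noncentrality is 0.28 × √80 = 2.50. A one-sided paired t-test at an assumed level of 0.05 then has 79.9% power, so the figure reproduces. No power shortfall is claimed; 0.28 SD serves below only as a yardstick.

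**2. Who the adherence analysis concerns.** Section 7.2 says of the post-IDEO phase that "participants will receive 3 sessions of PT a week for an additional 4 weeks". That is 3 × 4 = 12 sessions, one third is 4, and fewer than one third means 0 to 3. Section 10.6 speaks of pre- and post-IDEO sessions, so the denominator may differ. The conflict does not depend on it.

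**3. When an exit visit would fall.** Section 4 puts fitting (T1) 2–4 weeks after T0 and T2 four weeks later, so T2 is at week 6–8. It then says: "At 12 months following the completion of the PRIORITI program (T4), participants will be asked to return to the Study Center". T4 is therefore at week 58–60. With a window of up to 2 weeks, T4 opens at week 56–58, which is 50 weeks after T2.

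The T4 anchor is not the same throughout:

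| Place | T4 counted from | Weeks after T0 |
|---|---|---|
| Sections 4 and 6.3 | end of the program or of PT | 58–60 |
| Section 6.4.2 (sports and leisure item) | IDEO fitting, week 2–4 | 54–56 |
| Section 10.2 | enrollment | 52 |

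Even on the earliest anchor, an exit at week 8 comes 52 − 2 − 8 = 42 weeks before the window opens. An exit earlier in PT is further away still.

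**4. What the exit visit can supply.** The T4 procedures include all seven performance tests scheduled at T2 (Section 6.3.1, Appendix C). An exit near the end of PT could therefore supply the Aim 1 outcome, possibly inside the T2 window. An exit early in PT would not. In neither case does it give a one-year value of the performance tests, the SMFA or the VR-12. No text says whether an exit value counts as T2, as T4 or as neither. Section 6.3.6 is also worded for a participant who terminates, and it is unclear whether it covers removal by the study.

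**5. Size of the overstatement.** Let r of 85 be removed, and let their mean change be g SD below that of the rest, m. The mean over all 85 is [(85 − r)m + r(m − g)]/85 = m − (r/85)g. The retained mean m is therefore too high by (r/85)g.

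The documents give neither r nor g. Assumed values: g from 0.28 to 1.0, the span of effect sizes in Section 10.2, used only as a scale; and r up to 5, because Section 10.2 plans for under 5% dropout and 80 of 85 complete.

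| r (share of 85) | g = 0.28 | g = 0.6 | g = 1.0 |
|---|---|---|---|
| 0 | 0 | 0 | 0 |
| 3 (3.5%) | 0.010 | 0.021 | 0.035 |
| 5 (5.9%) | 0.016 | 0.035 | 0.059 |

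At r = 5 this is 0.016/0.28 = 6% to 0.059/0.28 = 21% of the design effect.

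**6. Effect on the adherence comparison.** If 5 participants fall below one third and all are followed, the means without and with them differ by (5/85)g, or 0.016 to 0.059 SD. If all 5 are removed, both runs use the same 80 people and the difference is exactly zero.

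**The case against.** The strongest reply is that the plan, read as a whole, does not intend to discard low adherers. Section 8.9 is permissive. Section 10.6 expressly plans to analyse participants with low attendance. The Retention section and Section 10.4 push the other way: investigators are paid by completed follow-ups, reasons for missing data are collected, and sites that miss their targets can be dropped. Attendance is documented at each session (Section 7.2), so it can inform the missing-at-random analysis as long as some low adherers keep outcomes. Expected dropout is under 5%.

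Most of this stands. It limits the size of the problem and rules out some stronger readings:

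- A reader might infer that low adherers must be removed, or that fewer than one third of sessions is the removal threshold. Section 8.9 requires no removal and names no threshold.
- A reader of Section 6.3 might infer that T3 and T4 have no date for someone who does not complete PT. Sections 4, 6.4.2 and 10.2 supply calendar anchors. They disagree, but they exist.
- A reader might infer a serious rise in false-positive findings. With a true mean of zero over all 85, 5 removed and a gap of 1.0 SD, the removed participants would have to change by −(80/85) × 1.0 = −0.94 SD, a marked worsening. Nothing in the documents suggests that, and Section 4 aims for a stable population.

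What the reply does not answer is that none of these provisions says follow-up continues after removal for non-adherence. The models in Section 10.4 rest on assumptions that the section itself calls untestable, and they do not replace outcomes that could have been collected.

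**Conclusion.** The point holds as an unreconciled conflict: Section 8.9 allows the study to lose outcomes that Section 10.6 needs. The early-termination visit, the retention measures and the missing-data models mitigate it only in part.

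The direction would favour the program if removed participants gain less than the others. That is plausible but not documented. The size is unknown and is zero if nobody is removed. With up to 5 of 85 removed and an assumed gap of 0.28 to 1.0 SD, mean improvement is overstated by at most about 0.02 to 0.06 SD, against 0.28 SD. This would not overturn a large effect. It is worth correcting because the remedy is cheap and because, without it, the adherence analysis could reassure falsely.

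**What to change.** - **Section 8.9:** state that non-adherence with therapy alone does not end outcome collection. T2, T3 and T4 outcomes are still sought and enter the primary analysis unless the participant withdraws consent.
- **Section 6.3.6:** state that an early-termination value obtained outside the T4 window is not used as the T4 value. Say also whether the visit applies to removal by the study, and whether its performance tests count as T2 when they fall in the T2 window.
- **Section 6.3:** reconcile the anchors in Sections 4, 6.3, 6.4.2 and 10.2, so that visits for participants who do not complete PT are dated from one calendar point, such as the scheduled end of post-IDEO PT.
- **Section 10.6:** report how many participants below one third of sessions contribute outcomes at each time point, and how many were removed under 8.9.

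These changes concern data collection only, not whether therapy or the brace continues. The cost is a few sentences, some extra follow-up effort at visits already planned, and possibly a lower reported mean improvement.

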8.10 Replacement of a Participant Who Discontinues Study Treatment N/A

9. MONITORING

9.1 Site Monitoring Plan

The METRC Coordinating Center will be responsible for site monitoring consistent with ICH/FDA guidelines. Monitoring will include a combination of remote and on-site visits of participating clinical research sites to review the individual subject records, including consent forms, case report forms, supporting data, and medical records (physicians' progress notes, nurses' notes, individuals' hospital charts), to ensure protection of study subjects, compliance with the protocol, and accuracy and completeness of records. The monitors also will inspect sites' regulatory files to ensure that regulatory requirements are being followed.

The site PI will make study documents (e.g., consent forms, case report forms) and pertinent hospital or clinic records readily available for inspection by the local IRB, the site monitors, the DOD, the Office for Human Research Protections (OHRP), or other regulatory authorities for confirmation of the study data.

9.2 Safety Monitoring Plan

9.2.1 Safety Review Plan by the DSMB

A DSMB is not required for this study. A Medical Monitor has been appointed and will review any SAEs, unanticipated problems involving risk to participants or others and all deaths.

10. STATISTICAL CONSIDERATIONS

10.1 Overview and Study Objectives

The primary objective of this study is to assess immediate and long-term improvements in functional performance and self reported outcomes following completion of the PRIORITI program.

Secondary objectives include documenting patterns of device use, use of ambulatory aids, shoe wear and patient reported satisfaction associated with the IDEO, and assessing economic impact of the PRIORITI program.

10.2 Sample Size Considerations

A total of 85 patients will be consented and enrolled by the military core METRC centers (approximately 25-30 from each center); data collected from these participants will be used to test the research hypotheses.

We anticipate a low dropout rate (<5%) because highly motivated individuals will self-select themselves into the program. We will also provide a modest compensation to participants who are not on active duty for their time and travel. For power calculations we assume we will have complete follow-up data on 80 of the 85 participants who enroll. All functional and satisfaction outcomes are continuous. In Specific Aim 1a and Specific Aims 2a and 2b, we plan to test for improvements in outcomes at a specified point in time after enrollment (8 weeks for Specific Aim 1a and 1 year for Specific Aims 2a and 2b) as compared to baseline. One-sided paired t-tests will be used. Differences in means between follow-up and baseline will be reported along with 95% confidence intervals. The proposed sample size yields 80% power to detect an effect size (mean of the difference in outcomes between follow-up and baseline divided by the standard deviation of the difference) of 0.28 (a modest treatment effect). To put this effect size in perspective, Patzkowski et al., reports effect sizes for FSST, TSA, SSWV-L and 40D of approximately 0.6, 0.7, 1.0 and 1.0, respectively.

Based on the above considerations, the targeted sample size for the study is 85 patients.

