8. Non-English speaking

Outcome measures

Physical impairment will be determined using objective performance measures of agility (4 step square test and Illinois Agility Test), strength and power (sit to stand test and timed stair ascent), speed (self selected walking speed and 40 yard shuttle run), and postural stability (single leg stance).

Levels of participation will be measured using self reported measures of return to usual major activity (work, active duty, school, home management) and the Paffenbarger Activity Scale (PPAQ) that measures participation in light, moderate and vigorous recreational or sports activities.

Patient reported function and health related quality of life as measured using the total and dimension specific sub scales of the Short Musculoskeletal Functional Assessment (SMFA).

Statistical analysis: We are interested in assessing immediate and long-term improvements in functional performance and self reported outcomes. One-sided paired t-tests will be used to test for improvements in outcomes, comparing baseline data to later outcomes. Differences in means between follow up and baseline will be reported along with 95% confidence intervals.

Analysis of costs and benefits of PRIORITI will include an analysis of costs and outcomes observed over a 12-month period as well as cost-effectiveness projected over the patient lifetime.

Safety monitoring: The Medical Monitor is responsible for monitoring serious adverse events (SAEs) as the study progresses to ensure patient safety. The Medical Monitor may convene a meeting of the DSMB to evaluate any SAEs that he/she determines require immediate attention.

Data Safety and Monitoring Board (DSMB): The DSMB is an independent body responsible for evaluating recruitment, safety and outcome data. The DSMB has the authority to stop the study based on its findings.

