6.4.2 Secondary Endpoints

Secondary Outcomes include additional self reported measures of participation, pain, depression and post traumatic stress. We will also be the use and satisfaction with the IDEO and related services.

- **Labor Force Participation and Work Productivity** will be assessed using standard questions used in other METRC studies. Participants will be asked what they were doing most of the time during the previous two weeks. If participants are working, the Work Productivity and Activity Impairment (WPAI) questionnaire will be administered. The WPAI measures work time missed and work and activity impairment because of a specified health problem during the past 7 days (for questionnaire: http://www.reillyassociates.net/WPAI_SHP.html)⁷¹. The validity of the WPAI has been established in a number of diseases⁷²⁻⁷³. In addition, the WPAI has proven a useful tool when measuring the relative difference between treatment groups in clinical trials and in subjects with and without disease.
- **Participation in Sports and Leisure Activities** will be assessed using the Paffenbarger Activity Scale (PAS)⁷⁴. At T0 (baseline) and at T4 (one year post fitting of the IDEO), patients are asked to identify up to 5 activities performed within the past 3 months. The 2000 version of the *Compendium of Physical Activities*⁷⁵ will be used to classify each activity according to its intensity level based on the rate of energy expenditure expressed as

metabolic equivalents (METS). Activities will then be classified as light (< 3 METS) moderate (3-6 METS) or vigorous (> 6 METS).

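### WPAI is asked only of people working at that visit, so the planned paired T0–T4 test would use only those in work at both visits and omit everyone who returns to or leaves work

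*Combined protocol and SAP*

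**What the plan says.** **Who answers WPAI.** Section 6.4.2 states: "If participants are working, the Work Productivity and Activity Impairment (WPAI) questionnaire will be administered". The same condition appears in the baseline interview list (6.2.3), the T3 list (6.3.4, carried forward to T4 by 6.3.5) and the Appendix C schedule, where WPAI is marked at T0, T3 and T4. Section 6.4.2 describes WPAI as covering missed work time, impairment at work and impairment of activity.

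**Which test applies.** The Protocol Summary states: "One-sided paired t-tests will be used to test for improvements in outcomes, comparing baseline data to later outcomes". Section 10.2 assigns this test to Aims 1a, 2a and 2b, and 10.6 repeats it for self-reported outcomes. Aim 2b compares patient-reported outcomes at T4 with T0. Appendix C lists WPAI, usual major activity and the Paffenbarger scale (PPAQ) among the self-reported outcomes.

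**The other participation outcomes.** The Summary includes "return to usual major activity (work, active duty, school, home management" as a measure of participation. Usual major activity is asked at T0, T3 and T4 whether or not the person works. For PPAQ, participants name up to five activities, and 6.4.2 continues: "Activities will then be classified as light (< 3 METS) moderate (3-6 METS) or vigorous (> 6 METS". No person-level score is defined.

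**Power.** Section 10.2 says "All functional and satisfaction outcomes are continuous" and then, assuming 80 complete pairs: "The proposed sample size yields 80% power to detect an effect size" (the mean change divided by its standard deviation) "of 0.28 (a modest treatment effect".

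**The concern.** Two rules, each reasonable alone, combine badly. A paired test needs a value at T0 and at T4, and WPAI yields a value only when the person is in work. Someone out of work at T0 and back at work or duty by T4 has no baseline value. Someone who leaves work has no T4 value. Both drop out of the comparison, and the second rule for staying in, being in work at T4, is itself an outcome the programme may influence.

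Section 10.6 names labour-force participation, return to duty and productivity among the ways the programme might bring economic benefit. A paired WPAI result says nothing about the people whose work status changed, yet it could be read as the productivity effect of the programme. The missing-data section (10.4) does not help: these values are not lost, they do not apply. The plan gives no rule for them.

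There is a smaller gap beside this one. Usual major activity and PPAQ are recorded as categories, and the plan does not say what number per person would enter a paired analysis.

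**Working it through.** **1. Reproduce the plan's figure.** Inputs from 10.2: 80 complete pairs, one-sided paired t-test, 80% power, effect size 0.28. The documents state no alpha; one-sided 0.05 is assumed because it reproduces 0.28.

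- Normal approximation: (1.645 + 0.842)/√80 = 2.487/8.944 = 0.278.
- Noncentral t, 79 df, critical value 1.664, noncentrality 0.28 × √80 = 2.50: power 79.9%; detectable effect 0.280.

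The figure holds for a numeric outcome with 80 pairs. At one-sided 0.025, power at 0.28 would be 69.6%.

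**2. Who has a WPAI pair.**

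| Work status at T0 | Work status at T4 | WPAI pair? |
|---|---|---|
| Working | Working | Yes |
| Not working | Working (returned) | No, T0 absent |
| Working | Not working (left) | No, T4 absent |
| Not working | Not working | No |

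Only the first row enters the test. This follows from the documents alone.

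**3. Illustrate the size.** The documents give no employment rates, so the share in the first row is assumed. Taking 45% to 62.5% of 80 gives 36 to 50 pairs. A wider range takes 40–80% working at T0, of whom 80–100% are still working at T4, which gives about 25 to 64 pairs (80 × 0.4 × 0.8 = 25.6; 80 × 0.8 × 1.0 = 64).

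| Pairs | Noncentrality 0.28 × √n | Power at 0.28 | Detectable effect (80% power) |
|---|---|---|---|
| 80 (plan) | 2.50 | 80% | 0.28 |
| 64 | 2.24 | 72% | 0.31 |
| 50 | 1.98 | 62% | 0.36 |
| 36 | 1.68 | 50% | 0.42 |
| 25 | 1.40 | 39% | 0.51 |

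**4. Count the people left out.** In a middle case (60% working at T0, 90% of them still working at T4, 20% of the others back at work, all assumed): pairs 80 × 0.6 × 0.9 = 43.2; returned to work 80 × 0.4 × 0.2 = 6.4; left work 80 × 0.6 × 0.1 = 4.8. About 11 people change status, and none of them contributes.

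**5. Is a paired t-test unsuitable for a yes/no activity variable?** A mean change in a 0/1 variable is a difference in proportions. In simulations with 80 pairs under no change, the one-sided 5% paired t-test rejected in 0.050–0.051 of runs at 10%, 20% and 40% discordant pairs; exact McNemar rejected in 0.020–0.036. Power under assumed gains and losses:

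| Gain / lose | Paired t | Exact McNemar |
|---|---|---|
| 15% / 5% | 66% | 57% |
| 20% / 8% | 66% | 59% |
| 20% / 5% | 88% | 84% |

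So the t-test is serviceable once a yes/no variable is defined. What has no meaning is a mean change across work, duty, school and home-management codes.

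**The case against.** A reader might infer that 10.2 wrongly declares every outcome continuous. It does not. Its sentence is confined to functional and satisfaction outcomes; nothing here shows it to be false for those, and it should stay. The defect is an omission about participation outcomes.

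A reader might also infer that the participation results as a whole would be invalid or would exclude people who return to work. The documents do not support that either. Usual major activity is collected from every participant at T0, T3 and T4, so gains and losses of work are recorded there. A yes/no version can be tested by the stated method with its error rate intact, and replacing it with exact McNemar would cost power. The plan never says that it will average category codes.

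The defence can add that Aim 2b does not name WPAI, that 6.4.2 makes participation secondary, that Aim 4 is descriptive, and that asking productivity questions only of workers is deliberate. All of this is fair and limits the weight of the point. It does not answer the WPAI problem: Appendix C lists WPAI as a self-reported outcome, the only before–after test named is a paired one, and the two rules together create the selected subset. Productivity at work can sensibly be asked only of workers, but activity impairment is not tied to having a job.

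**Conclusion.** The point holds for WPAI and is modest in weight. As written, its T0–T4 change can be estimated only in people working at both visits, a set that depends on a post-treatment outcome and contains no one who returned to or left work. That conclusion needs no assumption.

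Its size does. With 36 to 50 pairs, power at 0.28 is 62% at best and 50% at worst, and the detectable effect is 0.36 to 0.42; over 25 to 64 pairs, power runs from 39% to 72%. These figures assume the employment shares and a one-sided 5% test. The direction and size of any selection bias cannot be derived from the documents.

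For usual major activity and PPAQ, the gap is a missing person-level definition. The primary endpoints (performance tests, SMFA, VR-12), the 0.28 calculation and the target of 85 in section 10.2 are unaffected.

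**What to change.** 1. In 6.2.3, 6.3.4, 6.3.5, 6.4.2 and Appendix C, ask the activity-impairment part of WPAI of all participants at T0, T3 and T4. In 10.6, analyse its paired T0–T4 change in everyone.
2. Report the work-productivity parts as a description of those working at both visits, with their number. Beside it, report work or usual-activity status in all participants, showing gains and losses and the paired difference in proportions with a confidence interval.
3. Define usual major activity as a yes/no variable and PPAQ as a person-level numeric score, and analyse these in place of category codes.
4. In 10.2, keep the sentence on functional and satisfaction outcomes and add that the 0.28 power statement applies to numeric outcomes with about 80 pairs.

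A composite that scores non-workers as full productivity loss is not recommended as a required change: it needs a judgement on whether the limb caused the non-employment.

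Cost: analysis-plan wording and one extra question for non-workers at three contacts. The precision stated for WPAI work productivity becomes less favourable. Anyone whose T0 interview precedes the change and who was not working then would still lack a baseline value.
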